8.15 Drug Interactions/Precautions

AUR101 is metabolically stable molecule with low metabolism by CYP enzymes. It is neither a CYP inducer or inhibitor in in-vitro studies. So, drug interaction potential of AUR101 is low for CYP-mediated drug-drug interaction. Furthermore, AUR101 is neither a substrate nor an inhibitor of P-glycoprotein (P-gp) and Breast Cancer Resistant Proteins (BCRP) transporters.

9.0 STUDY ASSESSMENTS

This study is divided into 3 periods: Screening, Treatment, and Follow-up. The schedule of study procedures is presented in the Schedule of Events (**Table 1**). Window period for each visit is defined in the **Table 1**. All times should be recorded using the 24-hour clock (e.g., 23:20, not 11:20 PM). A description of individual study assessments is provided below.

9.1 Demographics and Medical History

Demographics and medical history will be obtained by the Investigator or designee during the Screening Period. Demographics will include date of birth (or age), sex, ethnicity, and race. Relevant medical history should be recorded and should include prior/current medical conditions, including psoriasis diagnosis, and abnormal physical exam findings or clinically significant laboratory abnormalities (excluding study disease-related abnormalities) from the baseline assessment.

9.2 Safety and Tolerability Assessments

9.2.1 Adverse Events

Monitoring and recording of AEs will be conducted and recorded throughout the study, starting from signing the ICF. Treatment-related AEs/SAEs that are ongoing at the time of Follow-up visit should continue to be followed until resolution, return to baseline, or until the investigator considers that further follow-up is not necessary. Definitions, documentation, and reporting of AEs are described in detail in Section

10.0.

9.2.2 Physical Exam and Vital Signs

A complete physical exam will be performed at every visit. Vital signs include temperature (oral or axillary), pulse rate and blood pressure (seated or supine for at least 5 minutes) assessed at every visit. One temperature method should be selected for each patient and used consistently at each assessment throughout the duration of study.

Weight will be recorded at every visit except visit 3, 5 and follow up visit. Height will be captured at screening only.

9.2.3 Clinical Laboratory Test

A blood sample will be taken for measurement of hematology and biochemistry parameters, and a urine sample will be taken for urine analysis at the following time points:

- Screening visit
- Randomization visit (Visit 2)
- Week 4, 8 and 12 (Visits 4, 6 and 7)
- Follow-up visit

In addition, viral serology tests will be performed at the screening visit. Following parameters (Table 6) will be measured:

Haematology	Biochemistry
Red blood cells	Alkaline phosphatase
White blood cells (WBCs)	ALT
Differential WBC count (absolute	AST
and %) including neutrophils,	Potassium
eosinophils, basophils, monocytes,	Serum Creatinine
lymphocytes	BUN
Haemoglobin	Sodium
Haematocrit	Chloride
Platelets	Bicarbonate
Mean corpuscular haemoglobin	Phosphorus
MCH concentration	Calcium
Mean corpuscular volume	Total bilirubin
	Albumin
	Globulin
	Total Protein
	Albumin/Globulin ratio
	Glucose
Urinalysis (on Visit 2 and visit 7 only	v)
Routine & microscopic examination	
Viral serology (For screening only)	
HBsAg, hepatitis C antibody, HIV I, H	IIV II

Table 6: List of Clinical Laboratory Tests

9.2.4 Electrocardiogram

Standard, single 12-lead ECGs at Screening and Follow-up visits will be performed. Heart rate and PR, QRS, QT, and QTc (Bazett) intervals will be entered in eCRF. During Screening, if the ECG reading shows any abnormality, it must be repeated two more times to confirm the findings, and then the patient should be assessed if (s)he should be ineligible for the study.

Machine read normal ECGs are acceptable for the study. ECGs read as abnormal by machine must be read by the PI / local ECG reader for final results.

9.3 Efficacy Evaluations

9.3.1 **Psoriasis Area and Severity Index (PASI)**

PASI is widely used tool to measure the severity of psoriasis. It combines area of the lesions with severity of individual lesions by grading erythema, induration/thickness and scaling. It can be 0 (minimum) to 72 (maximum).

For this study, an independent dermatologist at each site will evaluate PASI score at every visit for patients of the respective site. Additionally, PI will also evaluate PASI score independently.

A PASI score ^[25-27] will be derived as indicated in **Table 7**. The head, trunk, upper limbs and lower limbs are assessed separately for erythema, thickening (plaque elevation, induration), and scaling (desquamation). The average degree of severity of each sign in each of the four body regions is assigned a score of 0-4. The area covered by lesions on each body region is estimated as a percentage of the total area of that particular body region.

Body part	Erythema (E)	Thickening (plaque elevation, induration, I)	Scaling (desquamation, D)	Area score (based on true area %) [#]
Head (H) including neck	0=none 1=slight 2=moderate 3=severe 4=very severe	0=none 1=slight 2=moderate 3=severe 4=very severe	0=none 1=slight 2=moderate 3=severe 4=very severe	0 = 0% $1 = 1% - 9%$ $2 = 10% - 29%$ $3 = 30% - 49%$ $4 = 50% - 69%$ $5 = 70% - 89%$ $6 = 90% - 100%$
Trunk (T) Including axilla and groin area	0=none 1=slight 2=moderate 3=severe 4=very severe	0=none 1=slight 2=moderate 3=severe 4=very severe	0=none 1=slight 2=moderate 3=severe 4=very severe	0 = 0% $1 = 1% - 9%$ $2 = 10% - 29%$ $3 = 30% - 49%$ $4 = 50% - 69%$ $5 = 70% - 89%$ $6 = 90% - 100%$

 Table 7: PASI Score

Upper Limbs	0=none	0=none	0=none	0 = 0%
(U)	1=slight	1=slight	1=slight	1 = 1% - 9%
	2=moderate	2=moderate	2=moderate	2 = 10% - 29%
	3=severe	3=severe	3=severe	3 = 30% - 49%
	4=very severe	4=very severe	4=very severe	4 = 50% - 69%
				5 = 70% - 89%
				6 = 90% - 100%
Lower Limbs	0=none	0=none	0=none	0 = 0%
(L)	1=slight	1=slight	1=slight	1 = 1% - 9%
Including	2=moderate	2=moderate	2=moderate	2 = 10% - 29%
buttocks area	3=severe	3=severe	3=severe	3 = 30% - 49%
	4=very severe	4=very severe	4=very severe	4 = 50% - 69%
				5 = 70% - 89%
				6 = 90% - 100%

#Percentage (not score) of body region (not whole body) affected will be recorded.

Based on PASI, to be eligible a patient must have a score of 12 or more at screening and visit 2.

Based on total BSA, to be eligible, a patient must have 10% or more total BSA involved at screening and visit 2.

The following definitions are used in this study according to CHMP guidelines ^[16]:

- PASI 75 response: patients achieving ≥ 75% improvement (reduction) in PASI score compared to baseline are defined as PASI 75 responders
- PASI 50 response (partial response): patients achieving ≥ 50% improvement (reduction) in PASI score compared to baseline are defined as PASI 50 responders

9.3.2 Investigator Global Assessment (IGA)

The 5-point IGA mod 2011 scale has been developed based on a previous version of 6-point IGA/PGA Scale based on inputs received from regulatory agency ^[28].

The IGA mod 2011 used in this study is static, i.e. it refers exclusively to the patient's current disease state at the time of the assessments, and does not attempt a comparison with any of the patient's previous disease states, whether at baseline or at a previous visit. IGA mod 2011 will also be assessed by independent dermatologist and PI separately. Both the scores will be recorded in the eCRF.

The 5-point IGA mod 2011 rating scale is provided in **Table 8**. Based on this scale, a patient will be eligible to participate in the study if the patient has an IGA mod 2011 score of 3 or 4 at screening and Day 1.

Based on this scale, a patient will be considered as IGA 0 or 1 responder if the patient achieves a score of 0 or 1 and improves by at least 2 points on the IGA scale compared to baseline.

Score	Short Descriptor	Detailed Description
0	Clear	No signs of psoriasis; post-inflammatory hyperpigmentation may be present
1	Almost Clear	No thickening; normal to pink coloration; no to minimal focal scaling
2	Mild	Just detectable to mild thickening; pink to light red coloration; predominantly fine scaling
3	Moderate	Clearly distinguishable to moderate thickening; dull to bright red, clearly distinguishable to moderate thickening; moderate scaling
4	Severe	Severe thickening with hard edges; bright to deep dark red coloration; severe/coarse scaling covering almost all or all lesions

Table 8: The IGA mod 2011 rating scale [28]

9.3.3 Dermatology Life Quality Index (DLQI)

The Dermatology Life Quality Index (DLQI) is a 10-item general dermatology disability index designed to assess health-related quality of life in adult patients with skin diseases such as eczema, psoriasis, acne, and viral warts ^[29].

Scores range from 0 to 30, and higher scores indicate greater health-related quality-oflife impairment. Additionally, each subscale of the DLQI may be analyzed separately.

It will be completed in the language the patient is most familiar with, at the scheduled visit before he/she undergo clinical assessments by the investigator. The patient should be given sufficient space and time to complete the questionnaire. The principal investigator or designee should check the questionnaire for completeness and encourage the patient to complete any missing responses. The principal investigator or designee can explain the question, if required without influencing/guiding the response. The original questionnaires will be kept with the patient's file as the source document. Completed questionnaires will be reviewed and examined by the investigator at the site after the clinical examination and efficacy assessments for other parameters, for responses that may indicate potential AEs or SAEs. The investigator should review not only the responses to the questions in the questionnaires but also for any unsolicited comments written by the patient. If AEs or SAEs are confirmed then the investigator must record the events as per section 10.0. Investigator should not encourage or influence the patient to change the responses reported in the completed questionnaire.

9.3.4 Photograph of the lesions

PI should identify 1-2 index psoriasis lesions in each of the patients. At each visit indicated in Table 1, photography will be performed of these 1-2 index psoriasis

lesion(s) only. Index psoriasis lesion should have adequate severity (representative of overall severity, accessibility and re-evaluable at subsequent visits. If face (not preferable) lesion is required to be taken, then eyes must be masked or closed in all photographs. These photographs will be submitted to the sponsor to be retained as part of the patient's medical record; however, they will not be analyzed proactively, will serve as supportive in terms of overall evaluation and may be analyzed retrospectively, after the study is complete, should there be gross differences in the PASI assessments by the PI and the independent dermatologists, at any site. In that case as well, this analysis will not override the independent dermatologists' assessments.

9.4 Pharmacokinetics Assessments

9.4.1 Blood sampling

Patients who will consent to participate in the PK part, samples will be collected at pre-defined period till 12 hours after the dosing of Week 4 (± 2 days) visit. If required, metabolites of AUR101 can be assessed in the same samples.

Blood samples (4 ml) will be taken at the following time points relative to dosing, for PK analysis:

Time points: Pre-dose and 1, 3, 4, 5, 6, 8, 12 hours post-morning dose.

Window period for blood collection will be 15 minutes for pre-dose and ± 15 minutes for remaining time-points.

It is expected that approximately 25 patients will provide the PK sampling. For these patients, evening dose should also be given after collection of 12th hour sample.

Note: Dosing should be done after taking standard locally acceptable food.

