The MAD cohorts done with AUR101/placebo suspension in fed condition (with standard meal) showed T_{max} of 4-5 hours with mean terminal elimination half-life ranging from 14 to 22 hours. Based on C_{max} , AUC₀₋₂₄ and AUC₀₋₁₂, minimal increase in exposures was observed between 500 mg versus 1000 mg, suggesting that with a single time dose, peak in absorption likely occurs somewhere between 500 mg and 1000 mg. With BID dosing (600 mg BID), the C_{max} and AUC₀₋₁₂ substantially increased, when compared to both 500 mg and 1000 mg QD once daily regimens (Table 2). This is likely

because with increase in frequency of dosing (such as from QD to BID), AUR101 drug substance got two opportunities to be absorbed from the stomach, over 24-hour period, when an absorption kinetics plateau between 500 mg and 1000 mg with a single time dosing.

Parameter	Statistics	500 mg QD x14 days		1000 mg QD x14 days		600 mg BID x14 days	
		$(\mathbf{N}=0)$		(N=0)		((N=6)
		Day I	Day 14	Day I	Day 14	Day I	Day 14
C _{max} (ng/mL)	Mean (SD)	3711.95	4480.74	4394.89	5052.64	3597.27	7837.99
		(914.71)	(877.35)	(765.09)	(1239.83)	(1041.71)	(2945.57)
	Geometric	3614.32	4412.66	4338.06	4899.70	3469.26	7462.85
	Mean	(2763.07,	(3615.22,	(3597.84,	(3629.81,	(2538.19,	(5287.23,
	(95% CI)	4727.82)	5385.99)	5230.57)	6613.86)	4741.87)	1.05E+04)
T _{max} (h)	Mean (SD)	3.67 (0.52)	4.33 (0.82)	4.67 (0.52)	4.17 (0.98)	3.67 (0.82)	4.83 (0.41)
	Geometric Mean (95% CI)	3.63 (3.11, 4.25)	4.26 (3.44, 5.28)	4.64 (4.11, 5.24)	4.06 (3.12, 5.28)	3.60 (2.87, 4.50)	4.82 (4.38, 5.30)
AUC _{last} (h*ng/mL)	Mean (SD)	-	103718.11 (41883.94)	-	113826.95 (41124.24)	-	193019.87 (134249.01)
	Geometric		96480.30		107604.42		168381.87
	Mean	-	(6.19E+04,	-	(7.29E+04,	-	(9.81E+04,
	(95% CI)		1.50E+05)		1.59E+05)		2.89E+05)
		26977.52	39513.84	31584.64	40487.02	26713.79	71386.18
AUC0-12	Mean (SD)	(8038.07)	(10193.30)	(5962.66)	(10377.74)	(8654.54)	(30233.01)
(h*ng/mL)	Geometric	25928.42	38508.93	31054.65	39111.81	25557.68	67485.43
	Mean	(1.87E+04,	(2.98E+04,	(2.50E+04,	(2.84E+04,	(1.81E+04,	(4.72E+04,
	(95% CI)	3.60E+04)	4.97E+04)	3.86E+04)	5.39E+04)	3.60E+04)	9.65E+04)
AUC ₀₋₂₄		41323.55	64369.19	49727.38	65710.45		115400.32
(h*ng/mL)	Mean (SD)	(13348.11)	(19024.52)	(10147.46)	(20131.72)	-	(57173.33)
× 8 /	Geometric	39527.50	62152.73	48780.80	62758.16		107285.97
	Mean	(2.80E+04,	(4.60E+04,	(3.87E+04,	(4.35E+04,	-	(7.18E+04,
	(95% CI)	5.58E+04)	8.40E+04)	6.15E+04)	9.05E+04)		1.60E+05)

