3.4.1 Basis for Dose Selection

Repeat dose toxicology studies in rats and dogs for 13-weeks showed NOAEL doses of 450 mg/kg/day and 60 mg/kg/day (30 mg/kg BID) respectively. At higher doses in dogs ($60 \rightarrow 50 \rightarrow 40$ mg/kg BID), treatment related adverse findings were observed including severe clinical signs, body weight losses, low food consumptions, and increased ALT and AST. So, dog is considered more relevant and sensitive species.

The dosage and dosing schedule (BID) in the current Phase II study (AUR101-201) in patients with moderate to severe psoriasis is determined from the level and consistency of IL-17 modulation in the Phase I study (AUR101-101) (See Section 3.3) at different MAD cohorts. Specifically, in MAD Cohort 3 (600 mg PO BID x 14 days), the mean IL-17 level on Day 15 was $\sim 80\%$ below baseline value (Figure 3). This dose is, therefore, chosen as one of the two dosages in the proposed (AUR101-201) Phase II study. A lower dose (400 mg PO BID) is also proposed as investigating two separate dosages in Phase II will provide the risk-benefit analysis for two separate dosages and will help decide the dosage for Phase III.

The Day 14 human exposures, at 600 mg PO BID, is also compared with the NOAEL exposures, on Day 91 from the 13-week toxicology study in dogs. This comparison provides a 2.5-fold safety window (for 600 mg PO BID dose) and thus considered acceptable from safety perspective.

Table 4: Summary of Safety margin calculation based on NOAEL exposure in
animals and MAD exposure in humans

Study	Findings	Mean Exposure (AUC0- 24h) at NOAEL on the last day of dosing or Day 14 in MAD cohort 3 (hr*ng/mL)	Safety margin in humans with respect to NOAEL
13-week oral rat toxicity study	NOAEL 450 mg/kg/day	473472	3.3
13-week oral dog toxicity study	NOAEL 60 mg/kg/day	364160	2.5
MAD cohort 3 for 14 days	Dose 600 mg BID	142764#	-

HED = Human Equivalent Dose; NOAEL = No-Observed-Adverse-Effect Level. BID-= twice a day, MAD = Multiple Ascending Dose

[#]Mean AUC₀₋₁₂ on Day 14 was 71386.18 hr*ng/mL. Hence, AUC₀₋₂₄ is calculated as 2xAUC₀₋₁₂

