11.6 Pharmacokinetic Analysis

Individual plasma PK parameters, including but not limited to $t_{1/2}$, AUC₀₋₁₂, Kel, and CL/F. C_{max}, and T_{max} will be estimated using appropriate compartmental or non-compartmental models. Summaries of PK parameters will be presented by dose group.

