## 7.5 Pharmacokinetic (PK) Analysis

PK analysis will be performed on PK population.

Individual plasma PK parameters, including area under the concentration-time curve (AUC0-12), terminal elimination half-life (t1/2), maximum plasma concentration (Cmax), time to reach maximum plasma concentration (Tmax), elimination rate constant (Kel) and clearance (Cl) will be summarized and presented as described for continuous variables. Along with mean, SD, median and geometric mean concentration (GMC) and 95% GMC will also be provided by treatment arms.

Pharmacokinetic analysis will be performed only if sufficient patient's data are available.

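### Individual terminal half-life and Kel are to be reported from samples that stop at 12 h, about 0.46 of a half-life past the peak, so they will be imprecise and are probably short

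*Protocol*

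**What the plan says.** Protocol 9.4.1 sets one sampling day, the Week 4 visit: "Time points: Pre-dose and 1, 3, 4, 5, 6, 8, 12 hours post-morning dose". Nothing is drawn after 12 h, because the "evening dose should also be given after collection of 12th hour sample". On numbers: "It is expected that approximately 25 patients will provide the PK sampling".

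Protocol 11.6 lists half-life, Kel and CL/F with AUC0-12, Cmax and Tmax, and says that they "will be estimated using appropriate compartmental or non-compartmental models". SAP 3.2.4 repeats the list. SAP 7.5 describes the half-life as the terminal one and adds that "elimination rate constant (Kel) and clearance (Cl) will be summarized and presented as described for continuous variables". SAP 7.5 makes the PK analysis conditional on having enough patient data. Neither document sets an acceptance rule for a terminal slope (number of points, span or fit).

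For Phase I, Protocol 3.3 gives a Tmax "of 4-5 hours with mean terminal elimination half-life ranging from 14 to 22 hours". Those profiles ran well past 12 h: Table 2 reports AUC0-24 and AUC0-∞, and Table 3 adds AUC0-48.

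**The concern.** A terminal half-life is the slope of the log concentration once absorption and distribution are over. Here at most four samples (5, 6, 8 and 12 h) follow the peak, and the next dose closes the window before one half-life has passed. A line through those points measures the decline within the dosing interval, which need not be the terminal decline. At steady state the pre-dose sample approximates the 12 h trough, so it adds little.

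Plasma pharmacokinetics is a stated secondary objective. If the SAP is followed as written, the report will set a half-life labelled terminal beside Phase I values that came from much longer sampling. A shorter figure in patients could then be read as faster elimination in psoriasis when it reflects only where sampling stopped.

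**Working it through.** **Inputs.** Protocol Table 2, 600 mg BID, Day 14, geometric means: Cmax 7462.85 ng/mL, Tmax 4.82 h, AUC0-12 67485.43, AUC0-24 107285.97, AUC0-∞ 169987.05 h·ng/mL, t1/2 15.67 h (N = 6). Sampling times are from Protocol 9.4.1. Residual error per concentration is not in the documents; 5% to 15% is my assumption.

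**1. Does the Phase I half-life hold together?** For a mono-exponential decline after 12 h, let R = AUC24-∞/AUC12-24 and x = R/(1+R). Then t1/2 = 12·ln2/(−ln x).
- R = (169987.05 − 107285.97)/(107285.97 − 67485.43) = 62701.08/39800.54 = 1.575, so x = 0.612.
- t1/2 = 8.318/0.4915 = 16.9 h, against 15.67 h stated.
- The same step gives 16.1 h for 500 mg QD (14.48 stated) and 20.5 h for 1000 mg QD (21.37 stated).

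The stated range is consistent with the table. For BID this assumes no evening dose on Day 14. The documents do not say so, but the mean AUC0-24 of 115400.32 is well below twice the mean AUC0-12 (2 × 71386.18 = 142772.36), which supports it.

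**2. Window after the peak.** (12 − 4.82)/15.67 = 0.46 half-lives.

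**3. Shortfall, two-point version.**
- Terminal k = ln2/15.67 = 0.0442 per h.
- C12 = AUC12-24 · k/(1 − e^(−12k)) = 39800.54 × 0.04423/0.4119 = 4274 ng/mL.
- Apparent slope = ln(7462.85/4274)/(12 − 4.82) = 0.0776 per h, so apparent t1/2 = 8.9 h.
- Shortfall = 1 − 8.93/15.67 = 43%. Arithmetic means give 9.7 against 16.18 h, or 40%.

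Cross-check: if the terminal slope applied from the peak onward, AUC12-24 would be about 50,580. Table 2 implies 39,801. The fall before 12 h is therefore steeper than the terminal slope. Both QD cohorts show the same direction and need no assumption about an evening dose.

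**4. Shortfall, fit at the planned times.** A lagged bi-exponential was fitted to the Table 3 summary values (single 600 mg dose), with u = t − lag:
C(t) = A·e^(−αu) + B·e^(−βu) − (A+B)·e^(−ka·u).
For the tablet, A = 3906, B = 3105, α = 0.435, ka = 1.006, lag = 2.476 h, and β = ln2/15.14. Adding doses every 12 h to steady state gives about 7300, 6896, 6032 and 4811 ng/mL at 5, 6, 8 and 12 h. A noise-free log-linear fit returns 11.6 h against 15.14 h, which is 23% short. Across the tablet and suspension fits, with three or four points, the estimate is 11.5 to 11.7 h against 14.4 to 15.1 h, or about 20% short.

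**5. Precision, granting a perfect mono-exponential at 16 h** (k = 0.0433). CV(Kel) = s/(k·√Sxx). Sxx is 28.75 for 5, 6, 8, 12 h and 18.67 for 6, 8, 12 h. A half-life is within 20% of truth when Kel lies between k/1.2 and k/0.8, so the probability is Φ(0.25/CV) − Φ(−0.167/CV).

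| Residual error s | CV of Kel, 4 points | Half-life within 20%, 4 points | CV of Kel, 3 points |
|---|---|---|---|
| 5% | 22% | 66% | 27% |
| 10% | 43% | 37% | 53% |
| 15% | 65% | 25% | 80% |

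**6. Numbers per arm.** If the roughly 25 volunteers split 1:1:1, 25/3 ≈ 8 patients contribute per active dose. Neither document says that they will.

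**The case against.** Several points on the other side stand.

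- **Direction.** A short estimate does not follow from the 12 h cut-off alone. A one-compartment model with slow absorption would give a slightly long half-life (17.1 to 17.6 against 16.18 h). That model fits the protocol's data less well: it predicts Cmax/AUC0-12 of 0.093, while Table 2 gives 7837.99/71386.18 = 0.110. Short is the expected direction, not a certain one.
- **Size.** Applying step 3 to the QD cohorts gives 10.1 against 14.5 h and 7.6 against 21.4 h, so a reader might infer a shortfall of 30% to 64%. The documents do not support that for this trial. Both ends come from once-daily regimens that it does not use, and carry-over under BID dosing flattens the within-interval decline. The 43% is itself a two-point slope from Cmax to an inferred C12, built from differences of geometric means with N = 6. It is not the planned fit.
- **Precision.** The figures depend on a residual error that the documents do not give. At 5%, two thirds of four-point estimates are within 20% of truth.
- **Flexibility.** The protocol allows compartmental models, and the SAP makes PK analysis conditional on adequate data. Neither supplies terminal-phase observations. A model could do so only by borrowing the Phase I profiles, which the plan does not mention.
- **Consequence.** A reader might infer that dosing decisions are at risk. BID dosing was chosen on IL-17 inhibition (Protocol 3.3 and 3.4.1), the Phase III dose is to rest on risk and benefit of the two doses, and no stated decision uses a patient half-life.

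**Conclusion.** The point holds as a limited one about reporting. The planned samples do not observe the terminal phase, so half-life and Kel reported as terminal values will be unreliable. For the BID regimen the expected shortfall is roughly 20% (bi-exponential model at the planned times) to 43% (Cmax to C12 from Table 2, assuming no Day 14 evening dose). With 5% to 15% residual error, the CV of an individual Kel is about 22% to 65% from four points and 27% to 80% from three. With about 8 patients per active dose, averaging would reduce the noise somewhat but not the bias.

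The documents do not support saying that the half-life is certain to be short or cannot be estimated at all, or that the PK objective fails. AUC0-12, Cmax, Tmax and steady-state CL/F need no terminal slope, and no efficacy result depends on one.

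**What to change.** In SAP 3.2.4 and 7.5, and in Protocol 11.6 at the next amendment, either remove terminal half-life and Kel, or keep them only as apparent within-interval values with a statement that they are not comparable with Phase I. Report AUC0-12, Cmax, Tmax, the pre-dose trough and steady-state CL/F, and define the last as dose/AUC0-12 so that it does not depend on Kel. If a half-life in patients is wanted, an optional route is a population model that pools these samples with the Phase I data.

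Cost: two listed parameters are lost or relabelled, and the wording of both documents changes. Under Protocol 12.5 a protocol revision needs ethics approval before use, which is why it can wait for the next amendment. No new samples or visits are needed. The pooled model, if chosen, is additional analysis work.
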